2.0 ENROLLMENT PROCEDURES

2.1 ELIGIBILITY CRITERIA

- 2.1.1 INCLUSION CRITERIA
 - 2.1.1.1 Age: ≥3 years and ≤25 years of age
- 2.1.1.2 Diagnosis: Patients with NF1 and progressive plexiform neurofibromas that have the potential to cause significant morbidity, such as (but not limited to) head and neck lesions that could compromise the airway or great vessels, brachial or lumbar plexus lesions that could cause nerve compression and loss of function, lesions that could result in major deformity (e.g., orbital lesions), lesions of the extremity that cause limb hypertrophy or loss of function, and painful lesions. Histologic confirmation of tumor is not necessary in the presence of consistent clinical and radiographic findings, but should be considered if malignant degeneration of a plexiform neurofibroma is clinically suspected. In addition to plexiform neurofibroma(s), all study subjects must have at least one other diagnostic criteria for NF1 listed below (NIH Consensus Conference[9]):
 - 1. Six or more café-au-lait spots (≥0.5 cm in prepubertal subjects or ≥1.5 cm in postpubertal subjects)
 - 2. Freckling in the axilla or groin
 - 3. Optic glioma
 - 4. Two or more Lisch nodules
 - 5. A distinctive bony lesion (dysplasia of the sphenoid bone or dysplasia or thinning of long bone cortex)
 - 6. A first degree relative with NF1

In this study a plexiform neurofibroma is defined as a neurofibroma that has grown along the length of a nerve and may involve multiple fascicles and branches. A spinal plexiform neurofibroma involves two or more levels with connection between the levels or extending laterally along the nerve.

2.1.1.3 Measurable disease: Patients must have measurable plexiform neurofibroma(s). For the purpose of this study a measurable lesion will be defined as a

lesion of at least 3 cm measured in one dimension. There must be evidence of recurrent or progressive disease as documented by an increase in size or the presence of new plexiform neurofibromas on MRI. Progression at the time of study entry is defined as:

- A measurable increase of the plexiform neurofibroma (≥ 20% increase in the volume, or a ≥ 13% increase in the product of the two longest perpendicular diameters, or a ≥ 6% increase in the longest diameter) over the last two consecutive scans (MRI or CT), or over the time period of approximately one year prior to evaluation for this study.

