3.1.4 MONITORING TIME TO PROGRESSION AND RESPONSE

This phase II trial is designed to determine the time to tumor progression and response rate with R115777 in patients with NF1 and progressive plexiform neurofibromas. The primary endpoint will be time to progression. Each patient will undergo MRI imaging of all known disease prior to entry on study. At the time of study entry one to three progressing plexiform neurofibroma(s) will be identified as index lesion(s), and followed for progression and response using 1D-, 2D-, and 3D-MRI. Results obtained with 1D-MRI and 3D-MRI analysis will be compared to conventional 2D-MRI analysis for their ease and reproducibility. The imaging protocol outlined in Appendix 1 will be used each time MRI scans are performed to assess response to R115777. MRI scans are performed prior to cycles 1, 4, 7, 10, and then after every 6 cycles on each study phase. If a patient is removed from a study phase because of clinical evidence of disease progression, the MRI scans should be repeated if they had not been performed within the past 4 weeks.

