5.4 STATISTICAL CONSIDERATIONS

5.4.1 Subject Accrual

Subjects of both genders, from all racial and ethnic groups are eligible for this trial if they meet the criteria outlined in Section 2.1. To date, there is no information that suggests differences in drug metabolism or disease response among racial or ethnic groups or between the genders, indicating that results of the trial will be applicable to all groups. Most plexiform neurofibroma grow out of proportion to somatic growth for a period of time during childhood, but reach a plateau by the end of puberty. Efforts will be made to extend the accrual to a representative population, but in a phase II study with limited accrual, a balance must be struck between patient safety considerations and limitations on the number of individuals exposed to potentially toxic or ineffective treatments on the one hand and the need to explore gender, racial, and ethnic aspects of clinical research on the other. If differences in outcome that correlate to gender, age, racial, or ethnic identity are noted, accrual may be expanded or additional studies may be performed to investigate those differences more fully.

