5.4.2 STATISTICS AND FEASIBILITY

The primary objective of the study is to determine whether R115777 ("drug") is able to increase the time to progression of patients who have NF1 with progressive plexiform neurofibromas. The study will be conducted as a crossover, two-arm randomized, double-blind, placebo controlled trial. After being randomized to drug or placebo, patients will be followed until progression. Once patients have progressed (documented by MRI), they will be crossed over to receive the placebo if they originally

received drug, and drug if they originally received placebo. Because the time until crossover is dependent on time until progression, this differs from a classic crossover study, in which patients are followed on both treatment arms for a predetermined fixed period of time, evaluated, given a wash-out period, and then followed identically on the other agent. As such, results from the first placebo vs. drug period will be used to determine sample size, and will constitute the primary endpoint of time to disease progression. The natural history of the growth rate and range of plexiform neurofibromas is not well known. In addition to the analysis of time to disease progression on the first treatment phase, a paired comparison of the first and second treatment phase (each patient will serve as his/her own control) will be performed using appropriate non parametric methods. This analysis will also help provide additional information on the differences in the natural history of NF1, and also address the effect of other variables, for example age differences, which may impact on the growth rate of plexiform neurofibromas.

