Because the estimate of time to progression for patients eligible for this trial is approximately 6 months, it would be desirable to increase this time to 12 months. A one-tailed hypothesis will be used since it would only be considered interesting to see the improvement of drug compared to placebo. With 80% power and a one-tailed alpha=0.05, in order to detect a difference in median time to progression (during the first part of the trial) between the two arms of 6 vs. 12 months, 30 patients per arm are required (60 total) assuming 36 months of accrual and 12 months of additional follow-up following entry of the last patient. Kaplan-Meier analysis using log-rank statistics will be used to perform the required evaluation. We plan to replace patients who were diagnosed with a malignant peripheral nerve sheath tumor (MPNST) after enrolling on study, as these patients will not be evaluable for the primary outcome measure, which is time to progression of progressive plexiform neurofibromas. For this reason we will increase the accrual ceiling to 63 patients

Randomization of patients between the two study arms will be performed centrally by Orkand (See Section 3.1.1, 3.1.2). With more than one institution participating, it is expected that 20 patients per year can be entered onto the trial, with an expected accrual period of 3 years.

This trial will be monitored by the NCI/DCS Data Safety and Monitoring Board. Due to the projected accrual rate, it is expected that 3 interim evaluations and a final evaluation will take place at each of 4 consecutive annual meetings of the DSMB. Using the O'Brien-Fleming approach, if the p-values at the following evaluations are less than or equal to those tabled below, then the trial would be declared to have a statistically significant result; no further accrual would be required once such a determination has been made.

Evaluation #	Threshold p-Value (one-tailed)
1	0.00005

2	0.0039
3	0.0184
4 (FINAL)	0.0412

In addition, if, at any annual evaluation, a conditional power analysis indicates that there is a minimal chance of declaring a significant advantage to drug with the addition of the remaining planned patients based on results to date and the hypothesized results, then the DSMB may choose to close the study to further accrual.

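### The primary phase A log-rank test ignores age at entry, which the protocol itself links to tumour growth; if age is prognostic, power is lost that an adjusted test could partly recover

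*Combined protocol and SAP*

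**What the plan says.** Section 5.4.2 bases the primary comparison of time to progression on phase A: "results from the first placebo vs. drug period will be used to determine sample size, and will constitute the primary endpoint of time to disease" (quoted up to its last word). For the test it says "Kaplan-Meier analysis using log-rank statistics will be used to perform the required evaluation". No covariate or stratification factor is named there, and sections 3.1.1, 3.1.2 and 5.4.2 name none for the randomization, which is described only as central.

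The age range for entry is "≥3 years and ≤25 years of age" (section 2.1.1.1). Section 5.4.1 says that most plexiform neurofibromas "grow out of proportion to somatic growth for a period of time during childhood, but reach a plateau by the end of puberty". Age then appears once more in the analysis plan: the additional paired comparison of phases A and B is to "also address the effect of other variables, for example age differences, which may impact on the growth rate of plexiform neurofibromas". Date of birth is recorded on the eligibility checklist (Appendix 8 A).

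**The concern.** Progression is a volume increase of at least 20% (section 3.1.5), so anything that changes growth rate changes the primary endpoint directly. The protocol names age as such a variable, enrols across puberty, and uses age in neither the randomization nor the primary test. The paired analysis cannot improve the power of the phase A comparison.

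When a strong prognostic variable is left out of a log-rank test, the treatment effect on the pooled hazards is diluted and power falls, although type I error is unaffected. With 60 patients and roughly 50 events there is little power to spare. A real doubling of time to progression would be more likely to be missed, and the conditional power rule for early closure would rest on the same less efficient statistic.

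**Working it through.** **1. The plan's own figure.** Inputs from section 5.4.2: "With 80% power and a one-tailed alpha=0.05", medians 6 and 12 months (hazard ratio 0.5 if exponential), 36 months of accrual, 12 more of follow-up.

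- Events (Schoenfeld, 1:1): 4(1.645 + 0.842)² / (ln 0.5)² = 51.5, so 52.
- P(event) = 1 − [exp(−12λ) − exp(−48λ)] / (36λ), with λ = ln 2 / median. Placebo: 0.941. Drug: 0.790. Mean: 0.865.
- N = 52 / 0.865 = 60.1, against 60 stated. Power at N = 60 is 80.3%.

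The sample size is therefore right for patients who share one hazard within each arm.

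**2. Age alone, single test at 0.05.** Two age groups, 30% older (assumed), overall placebo median held at 6 months, hazard ratio 0.5 within each group, 40,000 trials per row:

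| Hazard, older vs younger (assumed) | Plain log-rank | Age-stratified log-rank |
|---|---|---|
| 1 | 79.4% | 77.3% |
| 0.67 | 77.5% | 77.4% |
| 0.5 | 74.2% | 77.2% |
| 0.33 | 66.4% | 76.6% |
| 0.25 | 60.5% | 75.5% |

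**3. With the looks and the scan schedule.** The protocol expects that "it is expected that 3 interim evaluations and a final evaluation will take place at each of 4 consecutive annual meetings of the DSMB", with one-tailed thresholds 0.00005, 0.0039, 0.0184 and 0.0412. Progression is seen only at scans: "MRI scans are performed prior to cycles 1, 4, 7, 10, and then after every 6 cycles on each study phase". With 28-day cycles these fall at days 84, 168, 252, 420 and so on. Simulation: 30 per arm; exponential times given age; overall placebo median 6 months; uniform accrual; looks at months 12, 24, 36 and 48; censoring at the last scan; ages uniform from 3 to 25 (assumed); 10,000 trials per row (error about 0.5 point). Power at a true hazard ratio of 0.5:

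| Hazard below 16 vs above (assumed) | Plain log-rank | Cox, continuous age, Efron ties | Log-rank stratified at 16 |
|---|---|---|---|
| 1x | 75.9% | 74.9% | 74.3% |
| 1.5x | 73.9% | 74.3% | 73.9% |
| 2x | 70.0% | 72.3% | 72.7% |
| 3x | 62.7% | 69.6% | 72.8% |
| 4x | 55.5% | 66.3% | 71.0% |

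The loss due to age is 75.9 − 70.0 = 5.9 points at 2x, 13.2 at 3x and 20.4 at 4x. Cox recovers 2.3, 6.9 and 10.8 of these.

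**4. Other age patterns.** Across five patterns (slowing at 16; slowing at 18; taper from 10 to 18; log-linear decline from 3 to 25; slowing at 16 with 75% of patients under 16) the Cox gain is 1.1 to 2.3 points at 2x, 2.2 to 6.9 at 3x and 5.2 to 10.8 at 4x. A stratified test cut at 10 years, when slowing is at 16, gains only 0.2, 2.7 and 5.5 points.

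**5. Type I error.** Overall, with no age effect and at 2x and 4x: log-rank 5.4, 5.0 and 4.9%; Cox with Efron ties 5.1, 4.9 and 4.7%; stratified at 16 5.2, 5.1 and 5.0%. Scan-based times are heavily tied, so the tie method matters: Cox with Breslow ties has type I error of 2.1 to 2.4% and only 64.3% power with no age effect.

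**The case against.** The plain log-rank is a standard, valid test, and the plan contains no error of logic or arithmetic here. The rest of the opposing case concerns size.

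- **The age effect is assumed.** At 1.5x the Cox gain (0.4 point) is within simulation error, and at 2x it is 1.1 to 2.3 points. Large gains need 3x to 4x. With uniform ages, 4x implies placebo medians of about 3.7 months below 16 and 14.8 months above. This stands.
- **Entry requires recent progression (section 2.1.1.3), which screens out tumours that have stopped growing.** This may well weaken the age effect. With 90% of patients under 16 (also an assumption) the Cox gain falls to about 0.2, 1.2 and 2.6 points at 2x, 3x and 4x. But entry growth may be measured over about a year, and section 1.2.8 notes that some tumours become static after a period of growth, so the mechanism is reduced rather than shown to be absent.
- **Part of the shortfall from 80% is not due to age.** Correct: about 4 points (80.3 to 75.9%) are present with no age effect.
- **The stratified figures flatter the method**, because the cut sits where the simulated hazard changes. Correct, and a reason to prefer continuous age.
- **A look may already have been held.** The document carries a 2009 date, section 1.2.8 calls the trial ongoing, and looks are annual. The documents do not say that a look took place, but the possibility limits what can be changed.
- **Age is not ignored.** True, but the paired analysis leaves the primary test as it is.

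**Conclusion.** The point holds as one of efficiency, not validity. The primary test leaves out an already recorded baseline variable that the protocol ties to growth of the tumour being measured. If the hazard is 2 to 4 times higher before the end of puberty, the plain log-rank loses about 6 to 20 points of power, and Cox adjustment returns about 1 to 11 of them across the age patterns tried. If age does not matter, adjustment costs about 1 point. These sizes rest on assumed age effects and age mixes, and the benefit is small if few post-pubertal patients enrol. The change is worth making because it is cheap and its downside is small; confidence in the size of the benefit is only moderate.

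**What to change.** If no unblinded look has taken place, amend section 5.4.2 along these lines:

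> The primary phase A comparison is a one-tailed test of treatment in a Cox model with treatment and continuous age at entry, using the Efron method for ties.

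Use the same statistic at every DSMB look, against the existing thresholds, and in the conditional power calculation. Keep the plain log-rank as a sensitivity analysis. A two-stratum log-rank with a prespecified age cut near the end of puberty is an acceptable alternative, but it depends more on where the cut falls.

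If an unblinded look has already been held, leave the log-rank as primary and prespecify the age-adjusted Cox model as the main sensitivity analysis.

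The cost is a short amendment and a matching change to the DSMB analysis program. No new data are needed. The price in power if age proves irrelevant is about 1 point for Cox and 1.3 to 1.6 points for the stratified version.

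### The efficacy thresholds headed one-tailed are not the declared one-tailed 0.05 O'Brien-Fleming boundary (they spend about 4.7%), and the stated 80% power leaves out the interim looks

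*Combined protocol and SAP*

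**What the plan says.** All the statistical inputs are in section 5.4.2 of the combined protocol and SAP.

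- **Sample size.** "With 80% power and a one-tailed alpha=0.05, in order to detect a difference in median time to progression" of 6 versus 12 months, the plan requires 30 patients per arm, "assuming 36 months of accrual and 12 months of additional follow-up following entry of the last patient". The test is the log-rank test on the first treatment phase. This statement does not mention interim looks.
- **Ceiling.** Patients later found to have a malignant peripheral nerve sheath tumor (MPNST) are to be replaced. "For this reason we will increase the accrual ceiling to 63 patients".
- **Looks.** "it is expected that 3 interim evaluations and a final evaluation will take place at each of 4 consecutive annual meetings of the DSMB".
- **Boundary.** "Using the O'Brien-Fleming approach, if the p-values at the following evaluations are less than or equal to those tabled below", the result is declared significant. The column heading begins "Threshold p-Value (one-tailed", and the entries are 0.00005, 0.0039, 0.0184 and 0.0412.

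The section gives no information fractions, no spending function and no cumulative alpha for the table.

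**The concern.** The DSMB would use these numbers to declare efficacy and end accrual, so the named method, the declared alpha and the table should agree. An O'Brien-Fleming boundary at equal looks has a constant z × √(look number), and the printed values, read as headed, do not. The stated 80% power also looks like a single-test figure, although the plan tests up to four times. At stake are the true error rate of the stopping rule and the accuracy of the power claim. A DSMB statistician who tries to rebuild the table from the stated method and alpha will not succeed.

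**Working it through.** **Inputs from section 5.4.2:** one-tailed alpha 0.05; medians 6 and 12 months; 30 per arm; 36 months' accrual plus 12 months' follow-up; four annual looks; the four thresholds. **Assumptions not in the documents:** exponential times (hazard ratio 0.5), uniform accrual, no dropout, looks at months 12, 24, 36 and 48. The optional futility rule is left out.

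**1. The plan's own figure.** Expected progressions per arm at month 48 are n × [1 − (e^(−12λ) − e^(−48λ)) / (36λ)], with λ = ln 2 / median.
- Placebo: 30 × [1 − (0.25 − 0.0039)/4.159] = 28.2.
- Drug: 30 × [1 − (0.5 − 0.0625)/2.079] = 23.7.
- Total: 51.9.

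The log-rank drift is ln 2 × √(51.9/4) = 2.497. Power for one final test is Φ(2.497 − 1.645) = 80.3%. Thirty per arm is therefore reproduced as a design with a single test.

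**2. Shape of the table at four equal looks, z × √(look number).**
- Read one-tailed, as headed: 3.89, 3.76, 3.62, 3.47 (not constant).
- Read two-sided: 4.06, 4.08, 4.08, 4.08 (constant within rounding; overall two-sided alpha 0.048).

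**3. What the declared boundary would be.** The critical value at information fraction t is C/√t, with C solved by recursive numerical integration so that total one-tailed alpha is 0.05. C is 1.733 at equal looks and 1.730 at the annual looks. For the annual looks, the same accrual model gives expected progressions of 7.4, 22.4, 40.3 and 51.9, that is, fractions 0.14, 0.43, 0.78 and 1.

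| Look | Printed | 0.05 boundary, equal looks | 0.05 boundary, annual looks |
|---|---|---|---|
| 1 | 0.00005 | 0.0003 | 0.000002 |
| 2 | 0.0039 | 0.0071 | 0.0042 |
| 3 | 0.0184 | 0.0227 | 0.0248 |
| Final | 0.0412 | 0.0415 | 0.0418 |

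**4. Other spacings.** The printed one-tailed values have constant z × √t only at fractions (1.737/z)² = 0.20, 0.43, 0.69 and 1. Total alpha there is 4.80%, and the 0.05 levels would be 0.00006, 0.0042, 0.0194 and 0.0428. A Lan-DeMets O'Brien-Fleming-type boundary forced to match looks 1 to 3 would end at 0.0439, not 0.0412.

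**5. Alpha of the printed table, used as labelled.**
- Equal looks: 4.67%.
- Annual looks, both medians 6 months (fractions 0.16/0.47/0.81/1): 4.57%.
- Annual looks, both medians 12 months (0.12/0.39/0.73/1): 4.76%.
- Progressions counted only at scheduled scans (section 3.1.4: "MRI scans are performed prior to cycles 1, 4, 7, 10, and then after every 6 cycles on each study phase"): 4.67% and 4.84% for the same two cases.

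**6. Power with the printed looks.** At 51.9 progressions it is 78.6%, at equal or annual looks alike. The loss is 80.3 − 78.6 = 1.7 points. If progression is dated at scheduled scans, 50.0 progressions are expected, and the two figures become 79.0% and 77.3%.

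**The case against.** The strongest reply is that nothing is broken. The plan declares a one-tailed 0.05, and the table keeps alpha below that in every case examined. The plan never promises to spend exactly 5%, and the final threshold is within 0.0003 of the equal-look value. This stands, and it is why the point is minor.

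A second reply is that the looks are annual, so failure of constancy at equal looks does not prove that the shape is wrong. That also stands as far as it goes: at 0.20/0.43/0.69/1 the printed values do have the O'Brien-Fleming shape. But total alpha is then 4.8%, not 5%, and those are not the fractions that the plan's own accrual and medians imply.

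A third reply is that 1.7 points of power lie within planning uncertainty. With the hazard ratio kept at 0.5, a placebo median of 7 months instead of 6 takes single-test power to 78.8%. Sixty-three evaluable patients would give 80.3% with the printed looks. Both figures are right, but the three extra places are reserved for MPNST replacement, so they cannot be counted on.

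A reader might infer from the digits that this is a two-sided table under the wrong heading, and that the thresholds are meant for two-tailed p-values. One-tailed alpha would then be 2.4% and power about 69%. The documents do not support that use: both the hypothesis and the column are stated to be one-tailed. The two-sided origin is only an inference from the pattern, and even that reading gives 0.048 rather than 0.05.

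**Conclusion.** The point holds, at minor severity. The table does not match the declared one-tailed 0.05 O'Brien-Fleming boundary at equal looks, at the projected annual looks, or at the one spacing that restores its shape. Used as labelled it is slightly conservative, with one-tailed alpha about 4.7% (4.6-4.8%). The stated 80% is a single-test figure. With the printed looks and 60 evaluable patients it is about 78.6%.

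A reader might go further and conclude that the stopping rule inflates type I error or that the trial is seriously underpowered. Neither follows: the alpha error is in the safe direction and the power shortfall is under two points.

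That the power calculation omitted the looks is inferred from the reproduction and from the silence of the sample-size statement. The power figures rest on exponential times, uniform accrual and no dropout.

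**What to change.** **Main change.** In section 5.4.2, confirm that the thresholds apply to one-tailed p-values. State the operating characteristics of the printed table: overall one-tailed alpha about 4.7%, and power about 78.6% with 60 evaluable patients. This costs a sentence or two and no patients. Restoring 80% under the printed looks would take about 54.1 progressions, or 60 × 54.1/51.9 = 62.5, so 63 evaluable patients before any MPNST replacement.

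**Optional change, if the full 5% is to be spent.** Replace the table with a one-tailed 0.05 O'Brien-Fleming-type boundary computed at each meeting from observed first-phase progressions. Power is then about 79%. At 7, 22, 40 and 52 progressions the Lan-DeMets version gives <0.000001, 0.0026, 0.0246 and 0.0424.
- The plan must then state the planned number of progressions. About 52 is derived here and is not in the documents.
- It must also say what happens if that number is exceeded. At 9, 26, 46 and 56 progressions the final threshold (0.0352) falls just below that of look 3 (0.0354). Those counts are close to what is expected if both medians are 6 months.
- Under 6 versus 12 months, the chance of crossing by look 2 falls from about 15% to 12-13%. By look 3 it rises from about 55% to 59-60%.
- The cost is one paragraph and one short calculation per DSMB meeting.

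**What not to do.** Do not print the equal-look levels as fixed thresholds for annual meetings. One-tailed alpha would be 4.91-5.15%, and up to 5.26% if progressions are dated at scheduled scans.

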Time to progression between the two study arms will be compared separately for the two periods of the cross-over study; initial treatment and second (crossover) treatment. Both comparisons will be reported in order to describe the effect of drug on this endpoint. In addition, because each patient will have received both placebo and drug, comparisons of time to progression can be undertaken between both treatment conditions, employing methodology for paired subject data in order to further interpret the findings.

The quality of life of patients treated with R115777 and placebo on this study will be assessed using the National Institutes of Health (NIH) Impact of Pediatric Illness (IPI) Scale (Section 1.2.8), and scores of patients will be compared using the paired t-test.

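### Section 5.4.2 reports the phase B between-arm comparison as a measure of drug effect, although only phase A progressors enter it and randomisation does not protect it

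*Combined protocol and SAP*

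**What the plan says.** The primary analysis is the first period only. Section 5.4.2 explains that crossover time depends on progression, so the trial is not a classic crossover, and it bases the endpoint and sample size on phase A. The design target is a "median time to progression (during the first part of the trial) between the two arms of 6 vs. 12 months".

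Later in the same section a second comparison is added: "Time to progression between the two study arms will be compared separately for the two periods of the cross-over study". Its purpose is stated as: "Both comparisons will be reported in order to describe the effect of drug on this endpoint". No caveat, restriction or adjustment is attached to the second period. The next sentence justifies a paired analysis on the ground that every patient will have had both treatments.

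Sections 3.1.1, 3.6.3 and 6.4 say otherwise: crossover follows progression on the first treatment. Follow-up is bounded, "assuming 36 months of accrual and 12 months of additional follow-up following entry of the last patient".

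No test is named for phase B. The only between-arm method in the plan is for the primary question: "Kaplan-Meier analysis using log-rank statistics will be used to perform the required evaluation". Applying it to phase B is a fair inference, not a stated plan.

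**The concern.** Randomisation balances the arms at entry to phase A. Entry to phase B depends on a post-randomisation outcome, progression before the cut-off, and the treatment under test affects that outcome. If the drug works, fewer drug-first patients progress in time, and those who do are more strongly selected for fast growth. They form the phase B placebo group. Placebo-first progressors, who are less selected, form the phase B drug group. If growth rate carries over between phases, the drug group then starts with an advantage.

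Phase B follow-up is what remains after phase A and the two-week washout, so slower patients are also observed for less time.

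The stake is interpretation. Two between-arm results would stand side by side as descriptions of one drug effect, and a reader could take the second as replication of the first.

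**Working it through.** **Inputs from the documents.** One-sided alpha 0.05, power 80%, medians 6 and 12 months, 30 patients per arm, 36 months of accrual plus 12 of follow-up (all Section 5.4.2); two-week washout (Section 3.1.1), taken as 0.5 month; entry to phase B only on phase A progression (Sections 3.1.1, 3.6.3, 6.4).

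**Assumptions, because the documents give no figures.** Uniform accrual; patient differences as a gamma frailty with mean 1 and variance θ from 0 to 2, shared by both phases; where growth slows, a hazard falling 1 to 4% per month from entry.

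**Step 1: the plan's own figure.** Schoenfeld events = 4(1.645 + 0.842)²/(ln 0.5)² = 51.5, so 52. With exponential times and follow-up uniform on 12 to 48 months, the event probability is 0.941 on placebo and 0.790 on drug, mean 0.865. 52/0.865 = 60.1. The stated 60 is reproduced.

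**Step 2: who enters phase B.** Without heterogeneity, about 28 of 30 placebo-first and 23.5 of 30 drug-first patients enter. With θ = 1 and phase A median m, survival is 1/(1 + t/m). Entry requires progression at least 0.5 month before cut-off, so

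P(enter) = 1 − (m/36) ln[(m + 47.5)/(m + 11.5)].

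- Placebo-first, m = 6: 1 − 0.1667 × ln(53.5/17.5) = 0.81.
- Drug-first, m = 12: 1 − 0.3333 × ln(59.5/23.5) = 0.69.

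Mean frailty of those entering = {1 − (m²/36)[1/(m + 11.5) − 1/(m + 47.5)]}/P(enter).

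- Placebo-first (phase B drug group): (1 − 0.0385)/0.814 = 1.18.
- Drug-first (phase B placebo group): (1 − 0.1030)/0.690 = 1.30.

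The phase B placebo group is the faster-growing one.

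**Step 3: effect on the estimates.** Simulation of both phases, 400,000 patients per scenario, Cox hazard ratios and Kaplan-Meier medians. Phase A medians are 6 and 12 throughout.

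| Frailty variance | Phase A HR | Phase B HR | Phase B medians, placebo/drug (months) |
|---|---|---|---|
| 0 | 0.50 | 0.50 | 6.0 / 12.0 |
| 0.5 | 0.59 | 0.53 | 4.9 / 10.4 |
| 1 | 0.65 | 0.55 | 4.0 / 8.9 |
| 2 | 0.72–0.73 | 0.58 | 2.7 / 6.3 |

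**Step 4: where the shift comes from.** If both phase B groups were drawn from the same progressors, the hazard ratio would be about 0.57 at variance 0.5, 0.60 to 0.61 at variance 1 and 0.65 to 0.67 at variance 2. Part of the gap from phase A therefore arises from conditioning on progression at all, and the rest from unequal selection. With unlimited phase B follow-up the medians are 4.9/10.7 at variance 0.5 and 4.0/9.1 at variance 1, almost the same as with the planned cut-off. Entry selection does most of the work on the medians.

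**Step 5: when it does not appear.**

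- *No drug effect (6 against 6 months).* Phase B HR 1.00 at every variance. One-sided rejection is 5.2 to 5.6% in 4,000 trials of 60. The medians still shorten, equally in both groups, to 5.2, 4.5 and 3.2 months at variance 0.5, 1 and 2.
- *Partial persistence, variance 1.* If half the patients redraw their growth rate at crossover, phase B is 0.60 against 0.65; if all do, about 0.65 in both phases.
- *Slowing growth, no heterogeneity.* The direction reverses: phase B HR 0.52 to 0.54 against 0.50, and phase B medians lengthen to 6.9–10.5 and 13.8–24.2 months.
- *Slowing of 4% per month with variance 0.5.* The hazard ratios nearly agree (0.56 against 0.57), and both medians lengthen slightly (7.3/16.8 against 6.8/16.4).

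**The case against.** A reader might infer that phase B necessarily exaggerates the drug effect. The documents do not support a fixed direction. Section 1.2.8 describes growth that is erratic over time, with rapid and quiescent periods, which argues against full persistence. Section 5.4.1 describes a plateau by the end of puberty, and slowing of that kind can cancel or reverse the shift.

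The benchmark matters too. In the gamma scenarios the patient-level hazard ratio is 0.50, and phase B at 0.53 to 0.58 is weaker than that. The overstatement is relative to the randomised phase A hazard ratio and to the ratio of medians. The absolute gap between medians falls, from 6.0 months to 5.6, 4.9 and 3.6 at variance 0.5, 1 and 2.

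Two other inferences are tempting. One is that phase B has an inflated type I error; the null simulations show it does not. The other is that informative censoring is the main fault; Step 4 shows that it adds little to the medians.

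The plan also protects itself in part, by making phase A alone primary and calling the second comparison a description. And phase B is imprecise: about 34 events at 60 patients, with a standard deviation of the log hazard ratio near 0.38. A shift from 0.65 to 0.55 is ln(0.65/0.55) = 0.17 on that scale, under half a standard deviation.

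All of this stands, and it limits the claim. It does not rescue the wording: the text describes the drug effect with a comparison that randomisation does not protect, and a bias of uncertain direction cannot be corrected by eye.

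**Conclusion.** The concern holds in a conditional form. Phase B is restricted to phase A progressors, entry differs by arm if the drug works (69% of drug-first against 81% of placebo-first at frailty variance 1), and follow-up is what phase A leaves. Section 5.4.2 gives no warning of this.

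If the drug works and growth rates persist within patients, phase B looks stronger than phase A (0.53–0.58 against 0.59–0.73 over frailty variance 0.5 to 2) and both medians are too short. The frailty variances, the degree of persistence and the slowing rates are assumptions. The documents describe heterogeneity and an age-related plateau but quantify neither, so the direction in this trial is likely at most, not established. The primary log-rank test and the sample size of 60 are not affected. The fault lies in how a supportive result would be presented and read.

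**What to change.** In Section 5.4.2, replace the sentence "Both comparisons will be reported in order to describe the effect of drug on this endpoint" with text to this effect:

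- The phase A log-rank is the only between-arm test of the drug effect.
- Phase B Kaplan-Meier curves are shown by treatment sequence as descriptive and conditional on phase A progression, with the number and percentage of each arm entering phase B.
- Phase B results are not used as confirmatory evidence of the drug effect.

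In the sentence that follows, limit the statement about having had both treatments to patients who progressed in phase A and crossed over.

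A joint model of both phases, with a patient frailty and terms for treatment and phase, may be added as a sensitivity analysis with its assumptions stated. It should not be the prescribed supportive estimate. Its hazard ratio is conditional on the patient and not directly comparable with the phase A one. It recovers a true 0.50 on gamma-exponential data (0.50 to 0.51). It gives about 0.45 to 0.47 when growth slows with time, where the true value is 0.50, or when growth rates are fixed per patient, where phase A gives 0.51.

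The cost is wording only. Phase B loses its standing as a separate comparison of drug with placebo.
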